13.2 Outcomes

The study objectives will be measured using the Outcome measures listed in the table below.

Objectives	Outcome Measures to be Completed		
Primary Objective			
To explore the therapeutic impact of	Knee flexion angle at initial		
Functional Electrical Stimulation	contact and midstance using an		
applied to either the Quadriceps	Electric Goniometer when walking		
during stance phase of gait or Tibialis	on a 5-meter level walkway and		
Anterior during swing phase of gait	going up and down the stairs		
over an 8-week period on variations	Quadricep and Tibialis Anterior		
of knee flexion at initial contact and	strength using a dynamometer		
midstance in children with crouch gait	Passive range of motion of knee		
and cerebral palsy.	flexion (popliteal angle), ankle		
	dorsiflexion and hip flexor length		
	using a goniometer		
	Hamstring, Gastrocnemius and		
	Rectus femoris spasticity		
	measured by Modified Tardieu		
	Scale (MTS)		
	Selective Motor Control as		
	measured by the Selective Control		
	Assessment of the Lower Extremity		
	tool (SCALE)		
Secondary Objectives			
To explore the immediate Orthotic	Knee flexion angle at initial		
effect of FES applied to either the	contact and midstance using an		
Quadriceps during stance phase of	Electric Goniometer.		
gait or Tibialis Anterior during swing			
phase of gait on variations of knee			
flexion at initial contact and			

Health Research Authority

midstance in children with crouch gait	
and cerebral palsy.	
3. To explore how FES applied to either	Hamstring, Gastrocnemius and
the Quadriceps during stance phase	Rectus femoris spasticity
of gait or Tibialis Anterior during	measured by Modified Tardieu
swing phase of gait effects strength	Scale (MTS)
of the Quadriceps and Tibialis	Quadricep and Tibialis Anterior
anterior and spasticity in the	strength measured using a hand
hamstrings, gastrocnemius and	held dynamometer
rectus femoris	
4. To explore how FES applied to either	Completion of the Selective
the Quadriceps during stance phase	Control Assessment of the Lower
of gait or Tibialis Anterior during	Extremity
swing phase of gait effects selective	
motor control	
5. To explore how FES applied to either	Parent and Child completion of
the Quadriceps during stance phase	the Gait Outcome Assessment
of gait or Tibialis Anterior during	List (GOAL) questionnaire
swing phase of gait over an 8-week	
period effects parents perception of	Child completion of the Neuro-
gait and CYP's perception of fatigue	QOL paediatric fatigue short form
and gait in children with CP and	and 12-Item Walking Scale
crouch gait	
	Post FES Semi structured
	interview with parents and
	children/young people exploring
	perception of FES intervention on
	gait function and mobility.
5. To explore the acceptability of FES	Semi-structured interviews
intervention and study participation	informed by the constructs
	,

	described in the Theoretical Framework of Acceptability
6. To monitor adherence to a an 8-week FES intervention with FES being applied to either the Quadriceps during stance phase of gait or Tibialis Anterior during swing	FES activity logger recordings of duration of use (HH:MM) and number of steps taken.
phase of gait in children with cerebral palsy and crouch gait.	Post FES Semi structured interview with parents and children/young people exploring barriers to adherence to FES intervention.

13.3 Outcome Measures

13.3.1 Primary Outcome Measures

Knee flexion at initial contact and midstance, measured by the Electrogoniometer when walking.

13.3.2 Secondary Outcome Measures

- Knee flexion, as measured by the Electrogoniometer, when ascending and descending the stairs
- PROM of the ankle, in a flexed and extended knee position using a goniometer
- PROM Popliteal angle of the knee using a goniometer.
- PROM of Rectus Femoris (Duncan Ely Test) using a goniometer
- MTS measuring spasticity in Hamstrings, gastrocnemius and rectus femoris
- Strength in the Quadriceps and Tibialis anterior using a handheld dynamometer.
- GOAL -Gait Outcome Assessment List
- Neuro-QOL paediatric fatigue
- 12 Item walking scale
- SCALE Selective Control Assessment of the Lower Extremity

14. DATA MANAGEMENT

14.1 Data Collection Tools and source document identification

Study data will be recorded on the trial specific case report forms. The Case report Form (CRF) will be a printed paper document. Data captured on the CRF will be considered source data. The baseline date and outcome measures that will be recorded are outlined in the data management plan.

The study co-ordinator will complete a CRF form for all participants. Completeness of data will be maximised by:

- Checking all forms at the end of the study to ensure no missing items
- Where possible, arranging another assessment session should the participant not attend the scheduled study appointment.

Once each study appointment is completed the CRF forms will be signed and dated by the SC.

14.2 Participant Numbering

Each participant will be issued a unique participant number once registered onto the study.

14.3 Archiving

Paper and electronic formats and essential study documentation (i.e content of Study Master file) will be store in a secure location for a minimum of 10 years after the end of the study. Archiving will be authorised by the Sponsor following submission of the end of study report. No essential documents should be destroyed unless or until the Sponsor gives authorisation to do so. This is in accordance with the University of Plymouth Research Data Management Policy which can be found here: https://plymouth.libguides.com/researchdatamanagement

14.4 Access to Data

The Chief Investigator will act as Data Custodian and will ensure that the location of the data and access to that data is shared with the Sponsor. Data will be collected and stored in accordance with the Data Protection Act 1998/General Data Protection Regulation 2018. Data generated from this study will be available for inspection on

Health Research Authority

request by the participating research team, University of Plymouth representatives, the REC, local R&D Departments, and the regulatory authorities. This is in accordance with the university of Plymouth's Research Data Management Policy which can be found here: https://plymouth.libguides.com/researchdatamanagement

15. STATISTICS AND DATA ANALYSIS

15.1 Quantitative data Analysis

Serial data (n=16) gathered across phase A and B will be analysed using multiple-methods including an extended celeration line (ECL), a percentage of overlapping data (PND) and a Two Standard Deviation Band Method .

The ECL or split middle line method can control for positive or negative trends in the A Phase. Here the Phase A data is divided into two halves and the median calculated for each half. The two median points obtained will be joined to form the ECL. The ECL is then extend through Phase B to predict any trend in the continuation of data. The number of intervention phase B data points above trend line will be counted and divided by total Phase B data points to calculate a percentage/ratio. A chance-level score is considered 50%, or 4 out of 8 intervention data points above the trend line [27].

The PND method is calculated by locating the highest data point plotted in the baseline phase A and then counting the number of intervention phase B data points that exceed it. This value is then divided by the total number of intervention phase B data points to calculate a percentage. A PND < 50% would mark no observed effect, PND = 50-70% signifies a questionable effect, and PND > 70% suggests the intervention was effective [28].

The two Standard Deviation Band Method involves calculating the mean and standard deviation (SD) from Phase A. The SD value will then be multiplied by two and then added to the mean to give the +2 SD band and subtracted from the mean to give the -2 SD band. A significant change in performance occurs when, within

Phase B, at least two consecutive data points fall outside the 2SD range within the intervention phase [29].

Data gathered at the start and end of each phase (n=4) will be summarised using descriptive statistics (median, range, inter-quartile range) and plotted. The graph will provide visual analysis and interpretation of trends, which will be compared alongside findings from serial measurement data analysis.

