[name], is a Clinical physiotherapy Manager and post-doctoral researcher, Torbay and South Devon NHS Trust. She will act as a co-investigator to the trial and overall, as a third supervisor for the part-time PhD studies of [name]. She will also provide guidance on the protocol; management of the study, data collection and analysis and write up and dissemination.

Patient representative will provide advice on the study protocol, patient/public facing documentation, recruitment, timelines, adverse events and finances and dissemination

The independent academic physiotherapist will provide advice on the study protocol, recruitment, and timelines, adverse events and finances and dissemination.

KEY WORDS

1.BACKGROUND

Cerebral Palsy is a neuromotor disorder that affects the developing fetal or infant brain and has prevalence of between 2 and 3 per 1000 births worldwide [1]. Although the injury to the brain is non-progressive the functional impairments associated with CP are progressive in nature, resulting in interrelated neuromuscular

Health Research Authority

impairments such as muscle weakness, spasticity, contracture and reduced selective motor control; these significantly impact on a child's walking pattern and community participation [2].[3]

The functional ambulatory status of children with CP is assessed using the Gross Motor Function Classification System (GMFCS). This is a five-level scale; children with GMFCS level I-II walk independently with some limitations, children with GMFCS level III use a walking aid and children with GMFCS level IV and V are reliant on a wheelchair [4]. This study will focus on ambulant Children with CP, GMFCS level I to III.

Crouch gait is the most common gait problem, affecting 72-76% of ambulant children with bilateral CP [5]. This highly inefficient, tiring gait pattern is characterized by excessive knee flexion during stance phase of gait and if left untreated can lead to chronic knee pain [6]. The cause of crouch gait and the degree of knee flexion is unclear and multifactorial in nature, with potential factors including but not limited to, knee extensors weakness, excessive tibial torsion, knee flexor spasticity and contracture and impaired Selective Motor Control (SMC) [5,7]

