Over time crouch gait leads to higher rates of joint pain, degenerative arthritis and if not adequately treated there is progressive gait deterioration. Once 30° knee flexion while walking is reached, the degree of crouch rapidly progresses leading to the child requiring wheelchair use for mobility [7]. Although crouch gait may affect relatively small numbers of children, its impact is felt across a child's lifespan, placing a heavy burden on their quality of life long into adulthood. Furthermore, the management of crouch gait spans from childhood to old age, requiring multidisciplinary intervention from physiotherapists, orthotist, and Orthopaedic surgeons, at a significant cost to the NHS.

At present, the treatment of crouch gait is dominated by surgical interventions with hamstring lengthening being the most frequently used approach [8]. This is usually performed in the later stages of childhood to prolong independent ambulation and when conservative treatment options are exhausted. However, computer modelling has identified that short hamstrings may not be the primary cause of crouch gait and hamstring lengthening surgery may further weaken already weak muscles, increase

Health Research Authority

anterior pelvic tilt and contribute towards back pain [8]. Furthermore, rates of hamstring lengthening revision are high, due to its limited effectiveness and a return of the crouch gait pattern [8]. This places a heavy financial burden on the NHS and is costly to both children and parents alike, who experience disruptions to their home and school life.

Conservative approaches to the management of crouch gait include botulinum toxin injections to the hamstrings, strength training of the lower limb extensor muscles and/or the prescription of orthosis such as Ground reaction ankle foot orthotics [7]. Evidence suggests that any benefit of conservative interventions to reduce the degree of knee flexion are usually short term, with inconsistent and/or variable outcomes on crouch [7]. The limited availability of successful conservative interventions for children with crouch gait means that surgery is almost inevitable, particularly if these children are to remain ambulatory into adolescence and even then, the rate of ambulatory decline in adults with CP is prolific [7].

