The lack of successful conservative intervention and high rates of ambulatory decline in children with crouch gait, highlight the need for further research into new novel treatment approaches such as Functional Electrical Stimulation.

2.RATIONALE

The focus of the proposed study is Children with GMFCS I-III, who comprise of around 67% of the population (about 23,400) of children with CP in the UK. Crouch gait is one of the most common gait deviations found in this population, affecting 72-76% of ambulant children with bilateral CP with the risk of it occurring increasing with age [9]. Over time crouch gait leads to higher rates of joint pain, degenerative arthritis and if not adequately treated there is progressive gait deterioration, loss of functional mobility and increasing reliance on a wheelchair for mobility. Although crouch gait may affect relatively small numbers of children, its impact is felt across a child's lifespan and places a heavy burden on a child's quality of life. Furthermore, the management of crouch gait spans from childhood to old age, requiring multidisciplinary intervention from physiotherapists, orthotist and Orthopaedic surgeons, at a significant cost to the NHS.

Health Research Authority

The lack of successful intervention and high rates of ambulatory decline in children with crouch gait, highlight the need for this research into FES. FES is a pocket electrical device combined with a foot switch to allow precisely timed muscle stimulation while walking. There is substantial evidence for the use of FES to manage ankle weakness (drop foot) in CP [10] and its use in this way is recommended in clinical practise by NICE [11]. In comparison, the evidence for using FES to address other gait abnormalities, such as crouch remains poor [7].

The use of FES to address crouch gait in children with CP has only been examined in two case studies [12, 13]. Both case studies reported that FES used to stimulate the quadriceps muscle increased knee extension during stance phase of gait and alleviated crouch.

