7.3.5 Walking Assessment

The walking assessment will take place across a 5-metre level walkway either in the child's home, local clinic room or University lab. The same setting will be used for each walking assessment pre and post usual physiotherapy and FES intervention. An electric goniometer will be placed over the knee joint (see figure 4) to measure the degree of knee flexion at initial contact and midstance in the most affected leg. An additional electrogoniometer will record ankle dorsi-/plantar-flexion and an accelerometer placed on the tibia to aid in the detection of initial contact while walking. Signals are sent via Bluetooth to a recording unit (Biometrics, DataLITE, UK) and analogue signal outputs are AD converted using a 1401 (CED electronics, Cambridge, UK) and recorded using Spike 2 software (version 6 CED electronics, UK).

To calibrate the electrogoniometer the output signal will be recorded while the participant is supine or sitting and the knee is passively positioned to 0 degrees and 90 degrees respectively (as confirmed using a manual goniometer). The most affected leg will be established through assessment of muscle length, spasticity and strength, taken during measures of impairment. At the pre 'Usual' physiotherapy care baseline assessment (Week 0) and the post 'Usual' physio care assessment (week 8) the CYP will be asked to complete an extensive walking assessment in the following three conditions 1.wearing their AFO's (if present) and normal footwear, 2. wearing their AFO and the FES pocket box (FES turned off and not connected to either lower limb muscle group), 3. Wearing No AFO (if safe to do so) and the FES pocket box (turned off and not connected to either lower limb muscle group), with each three conditions repeated three times (see figure 5A). In the pre 'FES' intervention and post 'FES' intervention assessment the CYP will be asked to complete the walking assessment in the following three conditions. 1. Wearing normal footwear and AFO, 2.FES ON and wearing normal footwear, 3. FES Turned off and wearing normal footwear, with each condition repeated three times. (see figure 5B).

Figure 4. Electric goniometer placement for walking and stairs assessment

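### Section 15.1 scores upward movement as benefit in the non-overlap and trend-line rules, but the primary outcome, knee flexion, improves by falling

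*Protocol*

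**What the plan says.** Section 15.1 applies three methods to the 16 serial measurements, 8 per phase.

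- **PND:** locate "the highest data point plotted in the baseline phase A and then counting the number of intervention phase B data points that exceed it", then divide by the number of Phase B points. Below 50% is the no-effect class, 50–70% is questionable, and above 70% suggests effectiveness.
- **ECL:** join the medians of the two halves of Phase A and extend the line into Phase B. "The number of intervention phase B data points above trend line will be counted" and expressed as a share, with 50% (4 of 8) as the chance level.
- **Two-SD band:** at least two consecutive Phase B points outside the Phase A mean ± 2 SD, on either side, count as significant change.

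The primary outcome in Section 13.3.1 is "Knee flexion at initial contact and midstance, measured by the Electrogoniometer when walking". Four places fix its direction:

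- Section 1 describes crouch as "characterized by excessive knee flexion during stance phase of gait".
- Section 1 also warns: "Once 30° knee flexion while walking is reached, the degree of crouch rapidly progresses".
- Section 1 describes the aim of conservative care when it says that "any benefit of conservative interventions to reduce the degree of knee flexion are usually short term".
- Section 2 reports that in earlier case studies FES "increased knee extension during stance phase of gait and alleviated crouch".

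Section 7.3.5 calibrates the electrogoniometer while "the knee is passively positioned to 0 degrees and 90 degrees respectively", and the recorded quantity is named as degrees of knee flexion. Nothing in the protocol re-expresses it as extension or reverses the count for any outcome.

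**The concern.** A rule that counts points above baseline suits an outcome where more is better, such as muscle strength. Knee flexion runs the other way. If the rule is followed literally, the children FES helps most score 0% on PND and the children who deteriorate most score 100%.

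The same problem reaches the weekly patient-reported measures in Section 9.2. The fatigue form rates how often symptoms occur and the walking scale rates limitations. On the item content higher looks worse for both, although the protocol does not give the scoring.

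The study has 12 single cases, no formal sample size calculation and no other quantitative test in Section 15.1. These per-child verdicts are therefore the main quantitative result, and the study is meant to inform a later randomised trial.

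**Working it through.** **The plan's own figure.** The ECL chance level is 4/8 = 50%. This reproduces: with no effect and a flat series, each Phase B point is equally likely to lie above or below the line.

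**Inputs from the protocol.** 8 points per phase and the PND, ECL and two-SD rules of Section 15.1. With 8 points, PND above 70% means at least 6 of 8 (75%), and PND below 50% means at most 3 of 8 (37.5%).

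**Inputs assumed.** The protocol gives no SD or effect size for knee flexion. Every shift and baseline value below is an assumption.

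**Step 1: one illustrative child.** Assumed baseline angles: 30, 32, 29, 31, 30, 33, 31, 30 degrees.

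- Maximum 33, minimum 29.
- Median of first half 30.5, median of second half 30.5, so the ECL is flat at 30.5.
- Mean 246/8 = 30.75; SD = √(11.5/7) = 1.28; two-SD band 28.2 to 33.3.

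| Phase B | PND as written (above 33) | PND reversed (below 29) | ECL above | ECL below | Two-SD rule met |
|---|---|---|---|---|---|
| All 10° lower (improved) | 0/8 = 0% | 8/8 = 100% | 0% | 100% | yes |
| Same as baseline | 0% | 0% | 50% | 50% | no |
| All 10° higher (worse) | 8/8 = 100% | 0/8 = 0% | 100% | 0% | yes |

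The inversion is purely logical. Whenever every Phase B angle lies below every baseline angle, PND as written is 0%, whatever the variance.

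**Step 2: how often this happens.** 200,000 simulated children per row, 8 + 8 independent normal points, shift in baseline SDs. The ECL is carried forward to weeks 10–17.

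| Shift in knee flexion | PND as written <50% | PND as written >70% | PND reversed >70% | ECL: over half above line | Two-SD rule met |
|---|---|---|---|---|---|
| −3 SD (better) | 100% | 0% | 92% | 4% | 96% |
| −2 SD | 100% | 0% | 57% | 12% | 73% |
| 0 | 96% | 0.3% | 0.4% | 47% | 10% |
| +1 SD | 63% | 11% | 0% | 68% | 28% |
| +2 SD | 16% | 57% | 0% | 84% | 73% |
| +3 SD (worse) | 1% | 92% | 0% | 94% | 96% |

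**Check of the null row.** With no effect, all orderings of the 16 points are equally likely. The probability that the top 6 are all from Phase B is C(10,2)/C(16,8) = 45/12870 = 0.35%. The probability that PND is below 50% is 1 − C(12,4)/C(16,8) = 1 − 495/12870 = 96.2%. Both agree with the simulation.

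**Naming.** Section 15.1 introduces PND as a percentage of overlapping data. The calculation described counts points that do not overlap, so the name states the opposite.

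**The case against.** Several counter-arguments deserve weight.

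- **Verdict labels attach only to PND.** For ECL the protocol gives a count and a chance level, so a score of 0 of 8 could be read as a clear departure below the line. This stands: ECL success is implied, not declared. The count is still in the unhelpful direction, and nothing says how a low score is to be read.
- **Only large worsening is mislabelled.** This also stands. PND as written calls a child effective in 11% at +1 SD and about 3% at +0.5 SD. In the other direction there is no such limit: an improved child almost always lands in the no-effect class.
- **The two-SD band would show the change.** It has an upper and a lower limit, and it flags 96% of children at a 3 SD shift in either direction. A reader could see which side was crossed. The rule itself does not call one side benefit and the other harm, so it would conflict with PND without resolving the conflict.
- **Stairs.** The protocol's account of crouch concerns walking, so one may doubt that less flexion on stairs is benefit. Section 4 includes stairs in the primary outcome at the same gait events, so the point does not rescue the rule. It does show that the direction must be stated there too.
- **An analyst would notice, or a statistical analysis plan would correct it.** Probably so in an exploratory study with plotted data. But this is an explicit rule, not an omission. A later plan must either inherit the error or contradict the protocol, and choosing direction after seeing the data is what pre-specification should prevent.

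**Conclusion.** The concern holds. As written, PND gives the wrong verdict on the primary outcome, and ECL counts in the wrong direction for it. The inversion rests only on the stated rule and on the protocol's own account of crouch; it needs no distributional assumption. The percentages (practically 100% of children with a 3 SD fall graded no effect; 92% and 57% graded effective at rises of 3 and 2 SD) rest on independent normal data and assumed shifts.

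For fatigue and walking limitation the reversal is likely but depends on scoring that is not given. For spasticity, scored as R2−R1, the direction is open. The misnaming of PND is a wording slip and adds no weight. Because the error concerns the primary outcome, it should be corrected before any serial data are analysed.

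**What to change.** Add a small table to Section 15.1 with one row per serial outcome, its direction of benefit and the matching rule:

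- **Knee flexion, initial contact and midstance:** PND = share of Phase B points below the lowest Phase A point; ECL = share below the projected line; two consecutive points below the lower two-SD limit = improvement, above the upper limit = deterioration. State explicitly that this covers stairs, or give stairs their own row.
- **Fatigue and walking scale:** the same downward rules, once the scoring is confirmed as higher is worse.
- **Strength:** keep the present upward rules, and read the two-SD band by side.
- **Spasticity (R2−R1):** state the sign convention and the direction for each muscle.

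Also say how an ECL share is to be interpreted relative to 50%, and correct the name to percentage of non-overlapping data.

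The cost is a few lines of text in a protocol amendment. No measurement, visit or sample size changes.
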